6.3. Health economic endpoints

Health economic endpoints will be evaluated during the study cycles:

- Number of days and daily doses of rescue medication administered for the treatment of CINV
- Number of re-hydration bags given for at least grade 2 vomiting (more details below)
- The number of days of unplanned hospitalisations related to CINV and department of hospitalization (type of ward)
- The number of outpatient physician visits and health care consultations due to CINV (e.g., general practitioner)
- The number of unplanned laboratory test including those at unplanned hospitalisations due to CINV
- Discontinuation of chemotherapy treatment due to CINV
- Delay of chemotherapy administration due to CINV
- Days of absence from work

The grade 2 vomiting is characterized in CTCAE version 5 as vomiting requiring intervention in the form of IV hydration. In this study, we will consider 2-5 vomiting episodes in 24 hours after chemotherapy administration as grade 2.

7. Definitions

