## 2. Introduction

Despite the development of important progress and evidence-based guidelines in chemotherapy-related nausea and vomiting (CINV), CINV management is far from optimal . Up to 40% of patients with cancer still present with uncontrolled CINV; CINV remains one of the most unpleasant side effects of chemotherapy . In our previous study, acute nausea and vomiting were reported by 37.3% of patients, while delayed symptoms were experienced by 47.1% of cancer patients . The burden that CINV places on cancer patients is considerable, thereby making it difficult for cancer patients to perform their daily life activities . CINV prevention remains to be an essential aim of antiemesis therapy, because CINV reduces patients' quality of life (QoL), has substantial adverse functional impact and has potential economic consequences in patients with cancer .

Antiemetic guideline recommendations are based on the emetogenic potential of chemotherapy and involve 4 levels of classification of intravenous chemotherapy agents, i.e., high, moderate, low and minimal; these have been accepted by major organisations . Moderate emetogenic chemotherapy (MEC) results in acute vomiting in 30% to 90% of cancer patients in the absence of antiemetic therapy . In addition to the chemotherapy type, several patient-related risk factors and clinical characteristics can increase CINV risk . These can include use of antiemetics inconsistent with international guidelines, younger age, prechemotherapy nausea, no complete CINV response in an earlier cycle, history of nausea/vomiting, (trait) anxiety, fatigue experience, and expectations of nausea/vomiting . Other studies have largely confirmed some of the key risk factors for CINV (history of vomiting during pregnancy, history of motion sickness, age, gender) and added other factors such as (chronic) alcohol consumption, body surface area, fewer hours slept the night prior to infusion, or advanced stage cancer . Currently, there is a limited consensus surrounding the most relevant patient risk factors that may predict CINV risk. Based on a recent study by Dranitsaris et al.  eight predictive factors have been identified, and an algorithm has been developed to combine these patient-related risk factors into the optimal treatment of prophylactic antiemetics. These include:

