### 3.5. Study Endpoints

Definition of the assessment of time-related study efficacy endpoints:

Time-related efficacy study endpoints assessment will start at time 0 defined as the start time of the chemotherapy administration on Day 1 of each of the three cycles.

CINV indicators, such as nausea and vomiting, their intensity and frequency and Quality of Life will be evaluated during the acute phase of emesis, from 0 to 24 hours from the start of chemotherapy, in the delayed phase of emesis, from 24 to 120 hours from the start of chemotherapy, and overall during each day (i.e., day 1, 2, 3, 4 and 5) from the start of chemotherapy.

The primary endpoint will be the proportion of complete responses (no emetic episode and no rescue medication), during the overall phase (0-120h), after the start of the MEC administration over three cycles of chemotherapy.

Clinical secondary endpoints will be evaluated during each cycle:

- Complete response during the acute (0-24h), delayed phase (>24-120h), overall (0-120h) and daily in each cycle;
- No emetic episode during the acute, delayed and overall phase and daily in each cycle;
- Number of vomiting episodes during the acute, delayed and overall phase and daily in each cycle;
- No rescue medication during the acute, delayed and overall phase and daily in each cycle;
- No significant nausea (maximum MAT scale = 2) during the acute, delayed and overall phase and daily in each cycle;
- No nausea (MAT scale = 0) during the acute, delayed and overall phase and daily in each cycle;
- Complete protection (no emetic episode, no rescue medication and no significant nausea) during the acute, delayed and overall phase and daily in each cycle
- Nausea and Vomiting-related quality of life indicators (through the Functional Living Index Emesis scale)
- Collection of chemotherapy delays and/or dose reductions (Delay of chemotherapy administration due to CINV will be also evaluated as part of health economic endpoints, see below)

Health economic endpoints will be evaluated during the study cycles:

- Number of days and daily doses of rescue medication administered for the treatment of CINV
- Number of re-hydration bags given for at least grade 2 vomitings (CTCAE v5)
- The number of days of unplanned hospitalisations related to CINV and department of hospitalization (type of ward)
- The number of outpatient physician visits and health care consultations due to CINV (e.g., general practitioner)

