## 3.7. Health Economics Outcome Research (HEOR) Assessments

The health economic component described in this clinical protocol will only focus on resource utilisation linked to CINV and treatment of events (efficacy/safety).

To capture event-related resource utilisation, patients will be followed for the duration of the study. If one of the following events occurs; death, withdrawal of consent, or lost to follow up, resource utilisation for these patients will be reported up to the point they are withdrawn.

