There are no changes from the Study protocol v5.1 (version from the 05-FEB-2024).

3. Activities to Be Done before Execution of Final Analyses

- The following tasks have to be done before final execution of analysis: Study database have to be locked (Status "read only"). All relevant data-management processes are finalized (approval by Project data manager or Project Manager).
- Disposition of patients in analysis sets and list of protocol deviations have to be approved.
- Assignment of adverse events to study treatment has to be approved.
- Coding of Adverse events and medical history have to be finalized and approved.
- A reconciliation of serious adverse events (SAEs), i.e. a comparison of SAEs in the clinical database and SAEs reported to the sponsor must be performed.
- Data from the Patient's diary, MAT questionnaire and FLIE questionnaire have to be digitalized, included in the clinical database and checked for discrepancies.

4. Study Objectives

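### SAP 6.3 replaces the protocol's CTCAE v5 criterion for the re-hydration endpoint with an unclear 24-hour episode count, and SAP section 2 does not declare the change

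*SAP*

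**What the plan says.** Protocol 3.5 lists the endpoint as "Number of re-hydration bags given for at least grade 2 vomitings (CTCAE v5"). It gives no episode count and no time limit within the cycle.

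SAP 6.3 keeps the same threshold, "Number of re-hydration bags given for at least grade 2 vomiting (more details below"), and then explains the grade in two steps. The first repeats the standard: "The grade 2 vomiting is characterized in CTCAE version 5 as vomiting requiring intervention in the form of IV hydration". The second sets a rule for this study: "we will consider 2-5 vomiting episodes in 24 hours after chemotherapy administration as grade 2".

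The observation period is wider than one day. SAP 6.3 opens with "Health economic endpoints will be evaluated during the study cycles", and Protocol 3.7 says "To capture event-related resource utilisation, patients will be followed for the duration of the study".

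SAP section 2 states "There are no changes from the Study protocol v5.1".

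**The concern.** The SAP describes the CTCAE grade by the need for IV hydration and then grades by counting episodes. These are different criteria, and they classify some patients differently. The endpoint counts bags, so a patient who received one for vomiting has already met the grade as the SAP describes it. An extra episode count can then only remove bags.

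The time phrase adds a second problem. It closely resembles the acute phase, which SAP section 6 defines as 0 to 24 hours from the start of chemotherapy. It also resembles the acute page of the MAT (Protocol Appendix 3), which asks about the 24 hours since chemotherapy. A programmer could reasonably restrict the rule to that window.

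At stake are one of the eight health-economic endpoints and the resource and cost comparison in SAP 9.6. If the arms differ in re-hydration for delayed-phase vomiting, the first-24-hours reading would hide that difference. Two programmers could also produce different tables from the same data.

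**Working it through.** The plan states no figure for this endpoint, so there is none to reproduce. The check sets the criteria side by side and classifies typical cases in which a bag was given for vomiting.

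**Inputs**
- Criterion P: CTCAE v5 grade 2 as SAP 6.3 describes it, namely vomiting that requires IV hydration. It has no count and no window.
- Criterion S1: the SAP count of 2 to 5 episodes, read as the first 24 hours after chemotherapy.
- Criterion S2: the same count, read as any 24-hour period after chemotherapy.
- Endpoint threshold: at least grade 2 (Protocol 3.5; SAP 6.3, 9.6.1 and the title of Table 14.4-2).
- Phases: acute 0 to 24 h, delayed 24 to 120 h (SAP section 6).

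**Classification of a bag given for vomiting**

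| Case | P | S1 | S2 |
|---|---|---|---|
| One episode, any time | counts | does not count | does not count |
| 2 to 5 episodes within 0 to 24 h | counts | counts | counts |
| 2 to 5 episodes in a later 24-hour period | counts | does not count | counts |
| 6 or more episodes within 0 to 24 h | counts | in by the threshold, no grading rule | in by the threshold, no grading rule |

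The first row departs from the protocol's criterion on both readings. The third row departs only if the window is the first 24 hours. The fourth row is a gap in the specification: the 2 to 5 range bounds grade 2, and the endpoint includes higher grades, but no episode rule says what those grades are. Code that tests only for 2 to 5 could miss these cases.

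**Share of the CINV observation window covered under S1**
- Covered: 24 / 120 = 0.20, or 20%.
- Without a grade 2 rule: (120 − 24) / 120 = 96 / 120 = 0.80, or 80%.

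Under S2 no part of the window is lost. These are shares of time, not of bags.

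**Does another SAP section settle it?** SAP 9.6.1 repeats the threshold without a rule. The title of Table 14.4-2 refers to CTCAE grade 5, where the protocol has version 5, and does not mention the episode count. One table therefore has two competing criteria.

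**The case against.** The best defence of the SAP has four parts.

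1. The time phrase can mean a rate per 24-hour period at any point after chemotherapy. That reading fits an endpoint assessed over the study cycles, and SAP 9.4 takes daily data after Day 1 from the diary. This stands: loss of delayed-phase bags is one reading, not a demonstrated exclusion. It does not rescue the single-episode case.
2. Protocol 10.3.1 generally keeps nausea and vomiting regarded as lack of efficacy, up to 5 days after dosing, out of the AE section. A CTCAE grade would then often be missing, and an episode count is a plausible substitute. The motive is understandable, but no AE grade is needed, because a bag given for vomiting already meets grade 2 as the SAP describes it.
3. Protocol 3.7.2 and 8.5 refer resource-use analysis to a separate Health Economics Analysis Plan, which is not among the documents. It may settle the window, but it would not remove the contradiction inside SAP 6.3.
4. The matter is small. This also stands: the primary endpoint, the sample size and the clinical secondary endpoints are untouched.

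Three stronger inferences are tempting, and the documents do not support them.
- A reader might infer that vomiting of 6 or more episodes drops out. The threshold of at least grade 2 keeps it in.
- A reader might take the background figures in Protocol section 2, "acute nausea and vomiting were reported by 37.3% of patients, while delayed symptoms were experienced by 47.1% of cancer patients", and compute 47.1 / (47.1 + 37.3) = 0.558 as the share of bags lost. Those are proportions of patients with symptoms in a previous study. One patient can belong to both groups, and neither figure concerns re-hydration.
- A reader might infer bias towards no difference, on the premise that NEPA's advantage is greatest in the delayed phase. Protocol 2.1 claims added benefit in the acute, delayed and overall phases and does not rank them.

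**Conclusion.** The point holds as an undeclared and internally inconsistent change of endpoint definition. That bags given after a single episode fail the SAP rule rests only on SAP 6.3's own description of CTCAE v5 grade 2. That delayed-phase bags fail it rests on the further assumption that the window is the first 24 hours, in which case 80% of the 0 to 120 h window in each cycle has no grade 2 rule. Above 5 episodes the fault is a missing grading rule, not an exclusion.

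The number of bags affected cannot be estimated from the documents, and neither can the direction of any bias between arms. The consequence is limited to this endpoint and the cost-efficacy analysis. It should be corrected before database lock, but it does not threaten the trial's main conclusion.

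**What to change.** Preferred: delete the episode-count sentence from SAP 6.3. State that all re-hydration bags given for vomiting during each study cycle are counted under the CTCAE v5 criterion named in the protocol, with neither a 24 h nor a 0 to 120 h limit. An hour limit would itself truncate an endpoint that runs over the cycles.

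Alternative, if an episode count is kept: apply it to every 24-hour period in the cycle, set the qualifying threshold at 2 or more so that higher counts are covered, and list it in SAP section 2 as a change from the protocol. This option asks more of the data. The diary covers Days 1 to 5 only, and each bag would need a date to be matched to a daily count. The health-economic form is not reproduced, so it is not known whether that date is recorded.

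In either case, correct the CTCAE reference in the title of Table 14.4-2, and check that the Health Economics Analysis Plan uses the same definition.

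The preferred fix costs one sentence and one table title. The protocol summary (Health Economics and Outcomes Research Assessments) says that these parameters are reported in the eCRF, so no new data collection appears necessary.

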7.1. Study Database and External Data

Data collected and validated in the clinical study database will be analyzed. Data from the Patient's diary, MAT and FLIE questionnaires will be digitalized to become a part of the clinical database. No other external data are planned to be used for the analysis.

7.2. Labels and Tags used in SAP and/or Outputs

The following labels will be used for the treatment groups:

- NEPA- the test arm (Akynzeo® (netupitant 300 mg /palonosetron 0.50 mg) + dexamethasone 8 mg)
- SoC- the control arm (one standard oral dose of one of the available 5-HT3 RA + dexamethasone 8 mg)

Notation of time points during the study should include the cycle and day number, e.g. „C2D1“ or „Cycle 2 day 1“.

Visits should be referred to as Visit 0/V0 for screening visit, Visit 1/V1 for visit at the start at Cycle 1 (correspondently for Visit 2 and Visit 3), and Visit 4/V4 for follow/up visit at the end of cycle 3.

7.3. General definitions

Treatment Start date is defined as the date (time) when a dose of antiemetic drug is administered.

Treatment end date is defined as the last day of Cycle 3.

The Investigational Medicinal Product (IMP) is defined (Directive 2001/20/EC) as a pharmaceutical form of an active substance or placebo being tested or used as a reference in a clinical trial, including products already with a marketing authorisation but used or assembled (formulated or packaged) in a way different from the authorised form, or when used for an unauthorised indication, or when used to gain further information about the authorised form.

IMP in this study is Akynzeo®, a fixed-dose oral combination (NEPA) of the NK1 Receptor Antagonist (RA) netupitant (300 mg) and of the 5-HT3 RA palonosetron (0.5 mg).

The non-IMP (NIMP) is defined as any medicinal products intended for research and development trials, which does not fall within the definition of an IMP.

Standard of care (dexamethasone, granisetron, palonosetron, ondansetron) used in Arm SoC and dexamethasone used in Arm NEPA is not fixed to a particular product. It is current standard treatment, based on national and international consensus, given according to local clinical practice for the CINV indication which is used regardless of whether the patient is being treated in the study or not. It is prescribed depending on patient's needs, according to the doctor's judgement and according to the availability in site. The patient may already be taking the standard care medicine(s) when entered into the study.

Standard of care will be used according to SPC and will reflect the consensus of experts in the evidence-based guidelines of MASCC ESMO resulting from systematic reviews of the published trials of the last two decades [7]. The dosages are perfectly in the range of dosages specified in SPC of these products.

Chemotherapy treatment (IV Moderately Emetogenic Chemotherapy) used in the study (alemtuzumab, azacitidine, bendamustine, carboplatin, clofarabine, cyclophosphamide, cytarabine, daunorubicin, doxorubicin, epirubicin, idarubicin, ifosfamide, irinotecan, oxaliplatin, romidepsin, temozolomide, thiotepa, trabectedina) in both arms NEPA and SoC does not fall within the definition of an IMP. These products are NIMPs used to assess relevant endpoints in the clinical trial, they will not be tested.

The end of the study for each patient is defined as the day of Visit 4. Visit 4 is a visit on Day 5 of Cycle 3 or before the start of the next programmed chemotherapy cycle. Visit 4 if the final visit of the study.

After participation in the study, the patient will be treated according to the common clinical practice based on the physician's discretion.

7.4. Baseline Values

A baseline is defined as the assessment collected at the baseline (screening, V0) visit. If there is no such value, the baseline will be missing.

7.5. Coded Terms and Used Dictionaries

Medical history and AEs will be coded using the Medical dictionary for regulatory activities (MedDRA).

7.6. Handling/Classification of Adverse Events

AEs will be classified with regard to their severity and relationship to the investigational medicinal product. Every effort must be made by the Investigator to categorize each AE according to its severity and its relationship to the study drugs.

The severity of an AE will be rated by the Investigator according to the descriptions and grading scales of the Common Terminology Criteria for Adverse Events (CTCAE) version 5, as follows:

- Grade 1 Mild; asymptomatic or mild symptoms; clinical or diagnostic observations only; intervention not indicated

- Grade 2 Moderate; minimal, local or non-invasive intervention indicated; limiting age-appropriate instrumental Activities of Daily Living (ADL)
- Grade 3 Severe or medically significant but not immediately life-threatening; hospitalization or prolongation of hospitalization indicated; disabling; limiting self-care ADL
- Grade 4 Life-threatening consequences; urgent intervention indicated
- Grade 5 Death related to AE

The causal relationship of an AE with the study drug will be classified as:

- Related
- Not related

If the Investigator's causality assessment is missing or unknown, the AE must be considered as related to the product.

7.7. Methods for Handling of Incomplete dates/times

No general imputation of dates/times will be performed except for the cases below.

7.6.1. AEs

If the time of the AE onset is missing and the date is the same as the start of treatment, the AE will be considered as starting after the beginning of the treatment.

If the day part of the date is missing and the month of the AE is the same as the month of the start of the treatment, the date of the first day of treatment will be imputed. If the AE occurs in a different month, the 1st of the month will be imputed, or if it is possible to determine a possible range of dates, the earliest date from this range.

If the month and/or year is missing from a date, and the month/year is the same as the month/year at the start of treatment, the date of start of treatment will be imputed. If the month/year is greater than the month/year at the start of treatment, the 1st of month/year will be imputed.

If the date is missing altogether, the treatment start date will be imputed.

7.6.2. Medical history

If the day/month is missing in the start date of the medical history issue, the 1st of the month/1st of the year will be imputed. If the day/month is missing in the stop date, the last day of month/last day of year will be imputed. If the stop date is missing completely, the issue will be considered as on-going. In case of the imputation of a stop date resulting in a date that is in future, the last day before the start of treatment will be imputed instead.

7.7.1. Concomitant medication

If the day and/or month is missing in the start date, the start of treatment will be imputed. If the day is missing in the stop date, the earlier date from last day of month/treatment end date will be imputed. If the month is missing in the stop date, the earlier date last day of the year/treatment end date will be imputed. If the stop date is missing completely, treatment with concomitant medication will be considered as on-going. In case of the imputation of a stop date resulting in a date that is in future, the last day before the start of treatment will be imputed instead.

7.8. Unscheduled/Repeated Assessments

In this study, the patients are followed for three consecutive cycles of chemotherapy. That is why the endpoint and secondary analysis will take into account a correlation between observations from one patient.

Unscheduled assessment should not occur and are not included in the CRF.

7.9. Rules and Formulas for Derived Variables

The CINV score will be calculated and used to identify patients with high risk of CINV. The calculation of CINV score will be done using following rules:

Predictive factor	Before a cycle of chemotherapy
Baseline score	10
Impact of patient risk factors	
Patient < 60 age	+1
Expectation (anticipation) of nausea and/or vomiting	+1
Patient has a history of morning sickness during a previous pregnancy	+1
Patient is about to receive platinum or anthracycline chemotherapy	+2
Patient used non-prescribed antiemetics at home in the prior cycle	+3
Patient has nausea or vomiting in the prior cycle	+5
About to receive the 2 nd cycle	-5
About to receive ≥ 3 rd cycle	-6

Since only the year of birth is available, the age of the patients will be calculated as the difference between the date of the screening and the first of January of the recorded year of birth.

The FLIE total score will be calculated from the corresponding questionnaire. The total score is the result of summing the responses to the 18 questions as the sum of the nausea and vomiting domain scores [5]. At least 12 of the 18 FLIE items (i.e., $\geq 66\%$ overall item response rate) must be non-missing, and both the vomiting and nausea domains must be non-missing, to calculate a FLIE total score. The score for domains (Nausea, Vomiting) will be also presented. At least 5 of the 9 FLIE domain items (i.e., $> 50\%$ overall item response rate) must be non-missing to calculate a FLIE nausea / vomiting domain score. Because the scale anchors are in the opposite direction on items 3, 6, 11, 15, and 18, the sensitivity analysis will be performed to assess the impact of incorrect responses. To assess the impact of these errors, the invalid item(s) will be set to missing before calculating the domain and total scores.

- Invalid nausea response: Set item 3 and/or 6 to missing if the item(s) are $\pm 50\text{mm}$ or more from the mean of items 1, 2, 4, 5, 7, 8, and 9.
- Invalid vomiting response: Set item 11, 15, and/or 18 to missing if the item(s) are $\pm 50\text{mm}$ or more from the mean of items 10, 12, 13, 14, 16, and 17.

The MAT scale for overall phase will be created by pooling the data from acute and delayed phases.

8. Flow of Patients and Specifications for analysed Populations

The flow of patients will be based primarily on analysis sets and if appropriate any other conditions which lead to exclusion of patients from total set of patients should be also included.

The following analysis sets are defined by the Study protocol.

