#### Risk scoring algorithm

Predictive factor	Before a cycle of chemotherapy
Baseline score	10
Impact of patient risk factors	
Patient < 60 age	+1
Expectation (anticipation) of nausea and/or vomiting	+1

CONFIDENTIAL

Confidential	MyRisk	Date: 05 February 2024
	Protocol	
	PROTOCOL NUMBER: IBA1160	Version: 5.1

Patient has a history of morning sickness during a previous pregnancy	+1
Patient is about to receive platinum or anthracycline chemotherapy	+2
Patient used non-prescribed antiemetics at home in the prior cycle	+3
Patient has nausea or vomiting in the prior cycle	+5
About to receive the 2 nd cycle	-5
About to receive ≥ 3 rd cycle	-6

VISIT 0 will be conducted within 2 weeks before chemotherapy administration on cycle 1 or alternatively on Day 1 of cycle 1.

- Verify Inclusion/exclusion criteria
- Collect the following information:
  - o Demographic data
  - o Primary cancer diagnosis
  - o Past and recent medical history
  - o Number of scheduled cycles
  - o Expected time between cycles
  - o Eastern Cooperative Oncology Group (ECOG) performance status (0, 1 and 2)
  - o Prior radiation therapy and site (within previous 3 months)
- Risk scoring algorithm will be calculated

RISK FACTORS (Risk scoring algorithm calculation)*	ADDITIONAL RISK FACTORS
Age	Gender
Expectation of nausea and/or vomiting (YES/NO)	Weight
Morning sickness during previous pregnancy (YES/NO)	Duration of sleep the night before chemotherapy
Chemotherapy type (platinum or anthracycline chemotherapy) and chemotherapy regimen details	History of nausea and vomiting other than morning sickness in females (not-chemotherapy dependent, e.g., motion sickness or vestibular dysfunction)
Use of non-prescribed antiemetics by patients at home in the prior cycle (YES/NO)	Anticipatory nausea/vomiting (CINV before chemotherapy) (YES/NO)
Nausea and/or vomiting in the prior cycle (YES/NO)	Alcohol intake (number of units per week)
Cycle about to be received	Fatigue experience (symptom) (YES/NO)
	Smoking status (YES/NO)
	Anxiety over the last 24 hours (to be inquired right before chemotherapy) (YES/NO)

\* Non-naive patient treated outside the study with any chemotherapy regimen at the previous cycles (the next cycle starts 6 months or more later after the previous chemotherapy treatment was finished), will be screened with the following answers to the CINV algorithm questions:

Cycle of chemotherapy about to be received: 1st cycle

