## 7. Data Collection and Data Management

IBA will manage all data management activities for the study.

Data will be collected into the database behind the EDC system **CLADE-IS** (see Appendix 6). The system has been specifically designed for the collection of large amounts of data in clinical trials and/or clinical registries. It will be fully customized to the structure and requirements of the project. The online application is accessible to users via any internet browser. Records are stored under a specific identity number (ID) which does not allow any backward identification of any individual patient. The unequivocal identification of the patient is only known to the treating physician or authorized healthcare professional.

Clinical management of the patient reflects the standard clinical practice in each country/center. Data (no patient's initials, no full date of birth will be collected) from all patients who meet inclusion criteria will be consecutively entered in the project database.

Each patient will fill the Patient's diary for 5 consecutive days after each chemotherapy administration, MAT questionnaire during the first 24 hours following chemotherapy, and four days after chemotherapy, and FLIE quality of life (QoL) questionnaire on 6th day after each chemotherapy. FLIE QoL questionnaire and MAT questionnaire will be available in validated translation for each country. Patient diaries will be available in local languages for each country. Patients included in the study shall undergo 3 consecutive chemotherapy cycles. Data from the Patient's diary and MAT will be digitalized onsite to become part of the electronic database. IBA will do the quality control process of digitalized patient diaries and MAT data. FLIE QoL questionnaires will be periodically sent to IBA for digitalization and following quality control.

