8.2. Protocol Deviations

List of protocol deviations (list of subjects to be excluded from the Per Protocol set) will be created and agreed before database lock and execution of statistical analysis.

For the Per Protocol set major protocol deviations will be reasons for exclusion. Minor protocol deviations do not lead to exclusion from Per Protocol set.

Following deviations will be monitored, but other deviations might also be considered after discussion:

- Any inclusion criterion not fulfilled.
- Any exclusion criterion violated.
- Study visits not corresponding to study design

9. Statistical Methodology and Specification of Sample Size

This section describes the data analysis in details. The statistical methods are planned in accordance with the study protocol and in accordance with ICH Topic E9 Statistical Principles for Clinical Trials.

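### SAP 7.9 counts age from 1 January of the birth year, so derived age is biased upward and about half of 59-year-olds lose the under-60 point in any risk score built on it

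*SAP*

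**What the plan says.** SAP 7.9 sets out the CINV risk score and says that it identifies high-risk patients. It then defines age by this rule: "the age of the patients will be calculated as the difference between the date of the screening and the first of January", where the January meant is that of the patient's birth year. The stated reason comes in the same sentence: "Since only the year of birth is available". Protocol section 7 gives the background: "no patient's initials, no full date of birth will be collected".

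The score starts at 10, and "Patient < 60 age" adds 1 (Protocol 3.6.3.1, repeated in SAP 7.9). Entry requires at least 13 (Protocol 3.3.1 and 3.6.3.2). Protocol 3.6.1 and 3.6.3 say that the eCRF computes the entry score automatically from factors 1 to 7, of which age is one. Protocol 3.6.3.1 lists age among the Visit 0 items. Neither document says how the eCRF obtains age for that calculation.

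SAP 8.2 monitors "Any inclusion criterion not fulfilled" as a protocol deviation. Major deviations exclude a patient from the Per Protocol set and minor ones do not.

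**The concern.** Nobody is born before 1 January of their birth year, so the rule can err in only one direction. A person aged 59 whose birthday is still to come in the screening year is counted as 60 or older and loses a point. The score is coarse and the threshold is sharp, so one point can separate 13 from 12. The age used in the tables, the under-60 flag and any score built on that flag all carry the same one-sided error. The plan has no correction or sensitivity analysis for it.

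**Working it through.** The plan gives no figure for age misclassification, so there is none to reproduce.

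**Inputs.**
- Age rule and score items: SAP 7.9.
- Threshold of 13: Protocol 3.3.1.
- Planned number, 410: SAP 9.2.
- Two assumptions, because the documents give no data: birth and screening dates are spread evenly over the year, and 2% to 4% of patients are aged 59.

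**Step 1: size of the overstatement.** Derived age minus true age equals the time from 1 January to the birthday. That is 0 to 365 days, with a mean of about 182 days (6 months). It is zero only for 1 January births.

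**Step 2: share of 59-year-olds who lose the point.** Let t be the fraction of the calendar year elapsed at screening. Among true 59-year-olds, a share 1 − t still have their birthday to come, and their derived age is 60 + t. The rest have derived age 59 + t. The share misclassified is therefore 1 − t.
- Mid-January: 1 − 0.5/12 = 0.96.
- Mid-December: 1 − 11.5/12 = 0.04.
- Averaged over the year: 0.50.

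A day-by-day calendar count gives 49.9% overall, 96% for January, 54% for June and 4% for December. A true 60-year-old has derived age 60 + t or 61 + t, so none gains the point.

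**Step 3: who sits on the threshold.** For a patient under 60 entering at cycle 1 with no prior-cycle items, the score is 10 + 1 + expectation (1) + morning sickness (1) + platinum or anthracycline (2).

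| Other factors present | True score | Without age point |
|---|---|---|
| None | 11 | 10 |
| Expectation only | 12 | 11 |
| Morning sickness only | 12 | 11 |
| Expectation + morning sickness | **13** | **12** |
| Platinum/anthracycline only | **13** | **12** |
| Platinum/anthracycline + expectation | 14 | 13 |
| Platinum/anthracycline + morning sickness | 14 | 13 |
| All three | 15 | 14 |

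Five of the eight profiles qualify, and two of those five drop out if the age point is lost. The same enumeration with the prior-cycle items finds exact-13 profiles in 3 of 14 qualifying profiles before a second cycle, and in 3 of 11 before a third or later cycle. These are counts of profiles, not of patients.

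**Step 4: number with a wrong flag.** 0.50 × 2% × 410 = 4.1, and 0.50 × 4% × 410 = 8.2, so about 4 to 8 patients under the assumed share.

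**Step 5: counting from 1 July.** Derived age becomes 59.5 + t for 59-year-olds with a birthday to come, which is wrong only when t ≥ 0.5. The average of 1 − t over that half-year, spread over the whole year, is 0.125. For 60-year-olds whose birthday has passed (share t), derived age is also 59.5 + t, wrong only when t < 0.5, and this again averages 0.125. The calendar count gives 12.6% and 12.4%. With similar numbers aged 59 and 60, total error falls from 50 + 0 to about 12.5 + 12.5 per hundred of each age, which is half.

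**The case against.** The rule is an openly stated consequence of not collecting full birth dates, and its reach is limited. Four stronger readings are tempting, and the documents support none of them as they stand.

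- **That eligible patients are being refused.** A reader might infer this because SAP 7.9 says that the score identifies high-risk patients. But 7.9 is a section on derived variables, entry rests on the eCRF's own Visit 0 calculation, and no text says that this calculation uses the 1 January rule. It may or may not.
- **That affected patients will be removed from the Per Protocol set.** This needs the score to be re-derived with SAP age, that score to replace the entry score in deviation checks, and the deviation to be graded major. Under SAP 8.2 the list is agreed before database lock, and Protocol section 7 has deviations classified and discussed at data review. Exclusion is possible but not automatic, and Per Protocol results are only supportive.
- **That 4 to 8 patients change eligibility.** That figure counts wrong age flags. Only those at exactly 13 cross the threshold. If the eCRF applies the rule, those patients are refused and are not among the 410.
- **That SAP 9.8 tests a corrupted candidate factor.** The candidates there are the nine additional factors. Age under 60 belongs to the existing set, against which the new set is compared.

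The primary comparison is also safe. Age is neither a stratification factor nor a term in the GEE model, and the rule treats both arms alike.

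All of this stands, and it makes the point small. It does not make the derived age right.

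**Conclusion.** The point holds as a low-priority correction. The rule biases derived age upward by about 6 months on average and misclassifies about half of true 59-year-olds in one direction. The half rests on evenly spread dates; by screening month the share runs from about 96% to 4%.

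The consequence for entry depends on something the documents leave open:
- **If the eCRF uses the rule,** 59-year-olds with a true score of exactly 13 score 12 and are refused.
- **If the site's true age decides,** eligibility is unaffected. A score re-derived under the SAP can still show 12 for an enrolled patient and be flagged as an unmet inclusion criterion, subject to the major/minor classification.

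In both cases age reported under the rule is too high. Wherever derived age is used, the under-60 item in the comparator score of SAP 9.8 is misclassified. The number affected cannot be computed from the documents. The range of 4 to 8 wrong flags in 410 rests on the assumed 2% to 4% aged 59, and threshold crossings would be fewer.

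**What to change.** 1. For the score and the analysis, use age in completed years, or an under-60 yes/no item, as recorded by the site at Visit 0. Where that record exists the misclassification is zero, and no birth date is needed.
2. State in the protocol or SAP which age feeds the automatic entry score, and that SAP-derived age does not override that score when deviations are assessed.
3. Where only the birth year exists, count from 1 July.

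The cost is one or two SAP sentences and, if the item is not already captured, one eCRF field. There are two downsides. A new field helps only patients not yet screened. And 1 July still puts about 12.5% of 59-year-olds at 60 or older and about 12.5% of 60-year-olds under 60. If it were used at entry, it could admit some patients whose true score is 12, so it is best kept as a fallback where no site record of age exists.
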